2.4.2.22 Balance and gait assessment

To further evaluate the effects of sensory restoration on balance control and gait stability, we will also perform a battery of clinically validated balance and gait stability metrics.

Assessments include but are not limited to the Sensory Organization Test (SOT), Functional Gait Assessment (FGA), and the Amputee Mobility Predictor (AMP). Metrics will be performed with and without stimulation to determine the effects of sensory restoration on balance control.

In the SOT, study participants stand on a platform that can impart translational and rotational perturbations at the feet, and key elements of sensory feedback (e.g. visual feedback, ankle proprioception) will be manipulated. By providing sensory feedback that is either unreliable or incongruent with the actual perturbation, the test provides a method for isolating the influence of somatosensory, visual, and vestibular inputs on balance. This test has been used to investigate balance control in individuals with lower-limb amputation²⁻⁵ and there is evidence that an amputee's ability to balance serves as a valid indicator of their fall risk² as well as their level of engagement in physical and social activities⁶.

The impact of sensory stimulation on walking can be quantified using Functional Gait Assessment (FGA). The final score of this metric has been demonstrated to correlate with risk of falling⁷. The FGA includes ten modules that evaluate gait on level surfaces with variable speed, horizontal and vertical head turns, obstacles, pivots, with narrow base of support, with eyes closed, and while ambulating backwards⁶. Implementation of the assessment involves an expert reviewer who scores each task for levels of impairment, walking path deviations, changes in velocity, stumbles, and losses of balance⁷.

The AMP can be used to the functional effects of sensory restoration⁸. The AMP encompasses many factors that contribute to an amputees' ability to ambulate with a prosthesis. The AMP is scored by an expert reviewer as the participant performs a number of activities including rising from a chair, transferring between chairs, standing balance, single limb balance, standing reach, initiation of gait, and stepping over obstacles and stairs⁸.

We will also perform posturography to quantify static standing balance². During this assessment, subjects will stand quietly on an instrumented force-plate while we record center of pressure under the feet. By quantifying changes in the movement of center of pressure over time, we can assess changes in static stability with sensory stimulation.

We will also perform posture and gait analyses, in which subjects will stand or walk while wearing optical motion capture markers to measure the kinematics and kinetics during quiet standing and gait.

All balance and gait experiments will be performed either under the direct supervision of a physical therapist or with the use of a safety harness system. Balance and gait experiments may be performed prior to device placement and up to one month after device removal as well as throughout the implant duration of the study.

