2.2 Study design

2.2.1 General study design

This study is a prospective, non-randomized, open-label, descriptive, interventional study.

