2.4.2 Experimental procedures

Pre-surgical procedures and device placement will occur within 6 months after the subject undergoes screening procedures. We will work with each individual to determine the optimal testing schedule. The schedule will be designed to meet study goals and complete specific study tasks which will change over the duration of the study. The participant's engagement and training preferences will also be considered in this process. We will photograph or videotape portions of the experimental session. Appropriate permission will be obtained as needed for any photographs or videotaping of participants. Female participants will be encouraged to avoid getting pregnant throughout the duration of the research study. Experimental procedures are described below.

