2.5 Study outcome evaluations

2.5.1 Study endpoints

The SCS leads will be removed no later than 90 days after implantation. The primary safety endpoint will be that there are no serious device-related adverse events. The secondary safety endpoint will be to determine the type and frequency of device-related

adverse events measured of the 90-day period following implantation. The primary efficacy endpoint for this study will be demonstration of the ability to evoke sensations localized to at least three focal regions of the missing foot and shank (e.g. lateral forefoot, medial forefoot, and heel). The secondary efficacy endpoints will be an improvement in balance control and gait stability and a reduction in phantom limb pain. Balance control and gait stability will be measured by a 10-point improvement in the Sensory Organization Test or a 6-point improvement in Functional Gait Assessment. A reduction in phantom limb pain will be measured by a 5-point improvement in the McGill Pain Questionnaire.

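### FGA and AMP are scored by a reviewer with stimulation on and off in an open-label study, with no rater masking or test order described, so expectation and order can contribute to the on-off difference.

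*Combined protocol and SAP*

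**What the plan says.** Section 2.2.1: "This study is a prospective, non-randomized, open-label, descriptive, interventional study".

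Section 2.4.2.22 sets the contrast: "Metrics will be performed with and without stimulation to determine the effects of sensory restoration on balance control". On the FGA it states "Implementation of the assessment involves an expert reviewer who scores each task for levels of impairment"; the sentence goes on to list observable signs (deviation from the path, velocity changes, stumbling, loss of balance). It also states "The FGA includes ten modules that evaluate gait on level surfaces with variable speed", among other conditions. On the AMP: "The AMP is scored by an expert reviewer as the participant performs a number of activities". The same section plans force-plate posturography and motion capture.

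Section 2.5.1: "The secondary efficacy endpoints will be an improvement in balance control and gait stability and a reduction in phantom limb pain". Balance and gait success is a 10-point gain on the Sensory Organization Test (SOT) or "a 6-point improvement in Functional Gait Assessment". No threshold is set for AMP.

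Section 2.4.2.21 leaves testing with the prosthesis to the investigator's discretion. Section 2.5.4 plans single-subject analyses, regression for performance with and without stimulation, and analysis of variance for scores before and after community use.

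Nowhere do the documents mention masking of the FGA or AMP scorer, or the order of the on and off conditions. Nor do they say who scores, who operates the stimulator during scoring, or whether the 6 points refer to on versus off or to before versus after.

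**The concern.** A score that rests partly on judgement, compared between two states that the scorer may know, can pick up the scorer's expectation. In a study of whether sensory feedback helps, that expectation is likely to favour the stimulated state.

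Order is a separate route. If stimulation is always tested second, practice adds to the apparent benefit and fatigue subtracts from it; if it is always tested first, the reverse holds. With order left open, neither the direction nor the size can be worked out afterwards.

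Two features of the plan make this matter. First, the word joining the two criteria in Section 2.5.1 is an or, so the reviewer-scored FGA can meet the balance and gait endpoint without support from the SOT. Second, about 10 subjects are to complete, analysed individually and without a concurrent control group, so a few spurious 6-point gains would change the reported result.

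**Working it through.** The plan has no figure to reproduce: it gives no SD of FGA change, rater bias, alpha or power, and Section 2.5.3 justifies the sample size as that of a feasibility study.

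**Inputs from the documents**
- FGA modules: 10 (Section 2.4.2.22).
- FGA threshold: 6 points (Section 2.5.1).
- Subjects intended to complete: 10 (Section 2.3.2).

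**Assumed inputs**
- Mean rater lean per module: 0.1 to 0.3 points.
- SD of one subject's FGA difference: 2, 3 or 4 points.
- True effect: none.
- Differences roughly normal and scores whole numbers, hence a continuity correction of 0.5.

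**Step 1. Lean as a share of the threshold.** Total lean b = 10 × lean per module; share = b / 6.
- 0.1 per module: b = 1, share 1/6 = 17%.
- 0.2 per module: b = 2, share 2/6 = 33%.
- 0.3 per module: b = 3, share 3/6 = 50%.

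**Step 2. Chance that one subject reaches 6 points.** p = P(Z > (6 − 0.5 − b) / SD).

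Worked for SD 3:
- b = 0: P(Z > 5.5/3) = 3.3%.
- b = 1: P(Z > 4.5/3) = 6.7%.
- b = 2: P(Z > 3.5/3) = 12.2%.
- b = 3: P(Z > 2.5/3) = 20.2%.

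| SD | b = 0 | b = 1 | b = 2 | b = 3 |
|---|---|---|---|---|
| 2 | 0.3% | 1.2% | 4.0% | 10.6% |
| 3 | 3.3% | 6.7% | 12.2% | 20.2% |
| 4 | 8.5% | 13.0% | 19.1% | 26.6% |

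Without the continuity correction, SD 3 gives P(Z > 6/3) = 2.3% for b = 0 and P(Z > 3/3) = 15.9% for b = 3. The pattern is the same.

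**Step 3. Chance that at least one of 10 independent subjects reaches 6 points.** 1 − (1 − p)^10.

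| SD | b = 0 | b = 2 |
|---|---|---|
| 2 | 3% | 34% |
| 3 | 29% | 73% |
| 4 | 59% | 88% |

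Section 2.5.1 does not say how many subjects must reach the threshold, so this step only shows how isolated responders could arise.

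**Step 4. Can the state be kept from the scorer?** Section 2.4.2.11 has stimulation delivered from an external stimulator. Section 4.1 allows the encoding to run on a connected PC. Section 3.1 already plans to switch the system off while a subject walks with a therapist supervising. The state can therefore plausibly be set out of the scorer's view. Because the scorer and the operator are not identified, this remains an inference.

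**The case against.** The strongest reply is that this is a descriptive feasibility study and the FGA is one of two routes to a secondary endpoint. The FGA also scores visible events such as stumbles, which leave less room for opinion. Force-plate and motion-capture measures do not depend on a rater, and the bias and SD used above have no source in the documents. All of this stands. It limits the weight of the point but does not remove it: grading impairment still takes judgement, and the FGA criterion can be met on its own.

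Several stronger readings are tempting but not supported:
- **That the scorer is known to be unmasked.** The documents call the study open-label and are silent on the scorer. What can be said is that no masking is described.
- **That masking needs no extra staff.** This is plausible, but the documents do not say who scores, who operates the stimulator or how many people attend.
- **That recordings already offer a fallback.** Section 2.4.2 says only "We will photograph or videotape portions of the experimental session"; nothing says FGA or AMP runs are filmed. A reviewer who was present and knew the state could recall it when rescoring.
- **That rater masking is the only protection.** A controlled test order and the instrumented measures also help.
- **That masking the on/off state protects the 6-point criterion in any case.** Section 2.5.1 does not tie the criterion to on versus off. If it means before versus after, the scorer would still know the time point.
- **That the threshold argument covers AMP.** It does not, since AMP has no threshold.

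**Conclusion.** The point holds with limited weight. As written, rater expectation and test order can both contribute to the on-off difference in FGA and AMP, and for FGA that difference may feed a declared secondary endpoint. The primary safety and evoked-sensation endpoints are unaffected.

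The size is illustrative. Under the assumed lean, up to half of the 6 points could come from the rater. The chance of a spurious 6-point gain rises with the lean at every SD tried, but its level depends heavily on the SD. The calculation shows what a lean of that size would do, not that one exists. It also assumes that the 6 points refer to on versus off, which the documents leave open.

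**What to change.** In Section 2.4.2.22, for on/off comparisons:
- The team member operating the stimulator sets the state from a pre-generated random or counterbalanced order.
- The FGA and AMP scorer is not told the state, where this is feasible and safe.
- Subjects are asked not to reveal the state.
- The scorer records a guess of the state after each assessment, so that the success of masking can be reported.

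In Section 2.5.1, state that the 6-point FGA criterion refers to this on/off contrast. If it is meant as a before/after change, note that masking the stimulation state does not protect it.

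Where live masking is not possible, report the FGA as unmasked and read it alongside the posturography and motion-capture results already planned. Rescoring by the same reviewer from recordings should not be the fallback.

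The cost is a few sentences of protocol text, an order list and one extra entry on the case report form. There are two downsides. Masking will be imperfect, because subjects feel the stimulation and may react visibly, and their own expectation remains. The change also assumes that the scorer and the stimulator operator are different people already on the team, which the sponsor should confirm.

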2.4.2.23 Electrode impedance

Periodically during experimental sessions, we will measure the impedance of the SCS leads as a means to ensure that the device is functioning properly. This functionality is included in the Abbott External Pulse Generator and the Ripple stimulator.

2.4.2.24 Clinic-based prosthetic training and assessment

Prior to each subject using the SCS-LLA system in the community outside the lab environment, one preliminary visit to the University of Pittsburgh's Physical Therapy Clinical and Translational Research Center (PT-CTRC) will be completed to determine the participant's baseline mobility, independence and function. This may include, but is not limited to, any relevant clinical evaluations of static and dynamic standing balance, gait and stairs. The participant's ability to perform transfers (sit to stand, stand to sit, etc.) may be assessed. These evaluations will not only serve as a baseline assessment of function, but will also determine the duration and type of training that will be required with the sensorized prosthesis.

Following SCS device placement and after stimulation parameters were selected for the SCS-LLA system, the participant will undergo 1-5 sessions of physical therapy and gait training with the SCS-LLA system and sensors attached to their prosthesis prior to the start of the community-use period. The duration of this training period will depend on the participant's baseline level of function and independence, their progression throughout the training, and the clinical judgement of an experienced physical therapist. During this period, the participant will perform tasks requiring varying levels of balance and dynamic stability in order to best prepare him or her for changes in environment during community use of the system. The primary purpose of this physical therapy assessment is to determine whether the participant can safely utilize the system independently.

In order to safely utilize the SCS-LLA system without assistance or supervision, the participant must be able to perform all necessary activities of daily living with modified independence (refer to checklist attached in **Appendix E**). Modified independence indicates that the participant is independent with the use of an assistive device. The participants must be able to safely maneuver curbs and thresholds. If the participant has stairs, either to enter or within their home, they should be able to ascend and descend steps independently, allowing the support of an assistive device or hand rail, if available in their home environment. Gait on uneven surfaces, over obstacles and up/down ramps will be tested and practiced, as well. The Amputee Mobility Predictor will also be used after training to determine K-level.

Assessment of functional independence and clinical judgement will be used to determine if the participant is safe to use the SCS-LLA system independently in the community. If the subject is determined to be a K-1 ambulator after training, they will be instructed to only use the SCS-LLA system within their home. K-2, -3, and -4 ambulators will be allowed to use the SCS-LLA both in the home and in the community. If, following 5 days of physical therapy, the participant is still not safe to use the system independently, in-laboratory testing with the SCS-LLA system will continue and the participant will not complete the week-long unsupervised portion of the community-use trial.

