2.4.2.25 Technical training and assessment

Prior to each subject using the SCS-LLA system unsupervised in the community outside of the lab environment, they will undergo training with lab staff on the proper use of the system, including techniques for donning and doffing, proper operation, calibration, and approaches for responding to system errors. Subjects will be instructed on various operating techniques, including:

- Connecting each component of the system and managing cables to avoid tangling or snagging on environmental hazards.
- Charging external batteries and connecting them to the Nomad
- Turning the system on and off and switching between operating modes (e.g. standby, calibration mode, active/stimulation mode)
- (Optional) Operating the smartphone application and using it to understand system state information (e.g. battery status) and control system parameters (e.g. enter calibration state, adjust peak stimulation intensity)
- Calibrating the system
- Responding to various error states (e.g. low battery, no stimulation, unexpected stimulation)

Before subjects are cleared for unsupervised community use of the system, lab staff will evaluate their understanding of system operations and approaches for responding to system error states, using the checklist in **Appendix E**. Supervised technical training may occur in the lab environment as well as during the two-week community use trial; however subjects will not be cleared for unsupervised community use until they have successfully demonstrated understanding of safe operating principals of the system.

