2.5.4 Outcome data and data analysis

The primary outcome measure of the study will be safety. We will track the rate of adverse events to monitor safety of the study. The primary efficacy outcome will be quantification and evaluation of the types of sensory percepts evoked by spinal root stimulation, as well as the anatomical locations to which those percepts are referred. Additionally, we will record any subjective changes in the perception of phantom limb sensations or phantom limb pain during and following spinal root stimulation. We will quantify differences in the ability to control a prosthetic limb with and without sensory stimulation. We will compare the balance and gait assessment scores of individuals using the SCS-LLA system and community-use of stimulation with the scores of subjects who underwent lab-only testing in our ongoing study to quantify the effects of extended access to the device.

New information will be learned with each participant, as this is a pilot study. Single-subject design statistical analyses will be used. Our main goals are to demonstrate device safety as well as the feasibility of using spinal root stimulation to evoke realistic sensory percepts referred to the foot and leg in individuals with lower-limb amputation, and to document any effects of that stimulation on phantom limb sensations and phantom limb pain. We will quantify the threshold for producing a just-noticeable sensory percept, as well as the relationships between stimulation parameters and evoked sensations when stimulating through individual electrodes or combinations of multiple electrodes.

To fulfill Specific Aim 1, we will document adverse events that occur during the study. We will report adverse events to the local Institutional Review Board and to the FDA in accordance with the respective reporting requirements. This documentation will serve as demonstration of the safety of the SCS-LLA system in this small sample.

To fulfill Specific Aim 2a, in which we quantify the threshold for evoking a sensory percept, we will use regression analysis to examine differences in stimulation thresholds related to a variety of factors. Examples of these factors include the anatomical location of each electrode (based on fluoroscopic imaging), level of amputation, time since amputation, level of pre-intervention phantom limb sensation and pain, and the thresholds of nearby electrodes.

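### The lab-only comparison does not say whether subjects not cleared for unsupervised use stay in the community-use group; dropping them would raise that group's balance and gait scores with no true effect

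*Combined protocol and SAP*

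**What the plan says.** The design is stated in Section 2.2.1: "This study is a prospective, non-randomized, open-label, descriptive, interventional study".

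Section 2.4.2.24 sets the functional clearance. After 1 to 5 therapy and gait-training sessions with the system, "the participant must be able to perform all necessary activities of daily living with modified independence", with assistive devices allowed. Curbs, thresholds and (where the home has them) stairs must be managed. Uneven ground, obstacles and ramps are tested and practised. "The Amputee Mobility Predictor will also be used after training to determine K-level". K-1 ambulators are restricted to home use; K-2 to K-4 may also use the system in the community. For a subject still not safe after five days of therapy, laboratory testing goes on and "the participant will not complete the week-long unsupervised portion of the community-use trial".

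Section 2.4.2.25 adds a technical check: "subjects will not be cleared for unsupervised community use until they have successfully demonstrated understanding" of safe operation. Section 2.4.2.26 puts a supervised period of community use before clearance.

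Section 2.5.4 says the investigators will "compare the balance and gait assessment scores of individuals using the SCS-LLA system and community-use of stimulation" and continues "with the scores of subjects who underwent lab-only testing in our ongoing study to quantify the effects of extended access to the device". It defines no analysis set for either side and describes no matching or adjustment.

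**The concern.** The clearance is applied after implantation, with the device in use, and it tests balance, gait and transfers. That is the domain of the scores compared in Section 2.5.4. If membership of the community-use group follows from who went on to unsupervised use, membership depends on a post-treatment result closely related to the outcome. The documents describe no comparable step for the lab-only subjects.

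A difference in favour of community use could then arise with no benefit from extended access, because the weakest performers with the system were left out on one side only. This is the only comparison the plan offers between extended access and lab-only use, so its reading matters even in a feasibility study. Because the plan is silent, the choice could also be made after scores are known.

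**Working it through.** **1. Where an uncleared subject can end up.** The text allows three readings.
- *Kept in the community-use group.* Possible, because supervised community use comes before clearance (Section 2.4.2.26), so the subject may already have used the system in the community.
- *Dropped.* Possible, because the stated purpose is the effect of extended access, and the subject missed the unsupervised week.
- *Counted as lab-only.* Possible, because Section 2.4.2.24 continues in-laboratory testing.

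The first gives no bias from the clearance. The other two remove the lower tail from the community-use group. The third also lowers the comparator's mean; I have not sized that addition because the comparator's size is not given.

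**2. Size if uncleared subjects leave the group.** The plan has no figure to reproduce: Section 2.5.3 rests on feasibility and gives no SD, effect size or power. The inputs below are therefore assumptions:
- f, the share failing clearance: 10% or 20% (one or two of the 10 subjects targeted in Section 2.3.2);
- ρ, the correlation of clearance performance with the balance or gait score: 0.5 to 0.9;
- normally distributed performance, with a hard cut at the f-quantile z.

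Mean shift of those who pass, on clearance performance: φ(z)/(1 − f). Shift on the outcome score: ρ × φ(z)/(1 − f), in SD units.

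| f | z | φ(z) | φ(z)/(1 − f) | × 0.5 | × 0.9 |
|---|---|---|---|---|---|
| 10% | −1.2816 | 0.1755 | 0.1950 | 0.10 | 0.18 |
| 20% | −0.8416 | 0.2800 | 0.3499 | 0.17 | 0.31 |

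With weaker correlations of 0.3 to 0.7, the same formula gives 0.06 to 0.14 SD at 10% failing and 0.10 to 0.24 SD at 20%.

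**3. On the scale of the Sensory Organization Test.** The documents give no SD. Assuming 10 to 15 points:
- at 10% failing, 0.0975 × 10 = 1.0 to 0.1755 × 15 = 2.6 points;
- at 20% failing, 0.175 × 10 = 1.7 to 0.315 × 15 = 4.7 points (products rounded from unrounded values).

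The improvement that Section 2.5.1 counts as a response is 10 points.

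**4. How likely the issue is to arise.** With 10 subjects, the chance that at least one fails is 1 − 0.9^10 = 65% if each passes with probability 0.9, and 1 − 0.8^10 = 89% at 0.8. If all 10 pass, the bias is zero.

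**5. Would baseline adjustment solve it?** Only in part. A pre-implant score removes the selection that baseline predicts. It does not remove selection on how a subject responded to the device and the training.

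**The case against.** The strongest reply is that the plan never says uncleared subjects are removed. The clearance bars them only from the unsupervised week, supervised use may already have taken place, and Section 2.5.4 speaks of community use, not of cleared users. This stands. A reader might infer that the plan excludes poor performers, but the text leaves the matter open, and the bias depends on how the gap is filled.

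A reader might also infer that the lab-only subjects passed no functional test. The documents do not establish that. Section 1.2 says only that the earlier work kept stimulation in the lab or clinic, with leads in for up to 29 days. A community-safety clearance would have had little purpose there, but the comparator's eligibility and screening are not described.

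Nor does the text support a contrast of good performers with unselected subjects. The clearance is a safety floor, K-1 ambulators can pass it for home use, and Section 2.3.3 already requires at least K-1 status at lead placement. Removing a lower tail still raises a mean, but this is not selection of an elite.

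The size also rests on assumptions, and a checklist with clinical judgement is not a hard cut on a normal score. With an assumed 10 subjects per group, the standard error of the difference is √(2/10) = 0.45 SD, larger than any shift in the table. The comparison also mixes in 1 to 5 therapy sessions and up to 90 against up to 29 days of lead placement. These facts limit how much the comparison can show. They do not justify leaving the group undefined, since a small sample does not average out a systematic shift.

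**Conclusion.** The point holds as a gap in the definition of the comparison. Section 2.5.4 groups subjects by use, use in the unsupervised week depends on post-treatment performance in the outcome domain, and the plan does not say what happens to those not cleared.

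If they leave the community-use group, its mean is raised by roughly 0.10 to 0.18 SD at 10% failing and 0.17 to 0.31 SD at 20%, given normal scores and a correlation of 0.5 to 0.9. If all are cleared, or all are kept, this bias is zero. The failure rate, correlation and SD are assumptions, since the documents give none.

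The analysis of variance before and after community use, planned for Aim 6 in Section 2.5.4, compares subjects with themselves and does not carry this between-group bias.

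**What to change.** In Section 2.5.4:
- State that the community-use group includes every subject of this study who reached the clearance assessment, cleared or not, each with laboratory scores at the same nominal time.
- Report how many were not cleared, and their scores separately.
- Adjust for pre-implant Amputee Mobility Predictor, Sensory Organization Test and Functional Gait Assessment scores where both cohorts have them.
- Label the comparison exploratory, naming the differences in therapy sessions and implant duration.

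Restricting both cohorts to the same post-training K-level is not a substitute. K-level decides home against community use, so it does not reproduce the clearance, and the restriction would itself condition on a post-treatment result.

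The cost is analysis wording and timed laboratory scores, drawing on the in-laboratory testing that Section 2.4.2.24 already continues. The clearance rule itself is untouched. The downside is dilution: if several subjects are not cleared, the estimated effect of access will be smaller than among those who had the full access.
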